9. TREATMENTS

Patients will be treated with any IOP-lowering agent to control the disease. The type and number of drugs will be decided by the treating clinician. Previous laser and/or surgery will be allowed but not within 6 months prior to study enrollment.

After signing of the informed consent form and ascertainment of eligibility, patients will be randomized in a 1:1 ratio to a Neurotidine[®]-placebo or placebo-Neurotidine[®] sequence and receive treatment for 3 months in the first period and for six months in the second period of the cross-over design. The second period will be extended to 6 months in order to control for potential carry over effect in the group receiving Neurotidine[®] in the first period of the cross-over design.

Neurotidine[®] 500 ml oral solution contains citicoline free acid 50 mg/ml; water; fructose; acidity regulators: sodium citrate, sodium hydroxide; preservative: potassium sorbate; color: riboflavin.

Placebo 500 ml oral solution contains water, fructose, sucralose; acidity regulators: sodium citrate, anhydrous citric acid, sodium hydroxide; preservative: potassium sorbate; color: riboflavin.

In addition to the IOP-lowering medications, Neurotidine[®] or placebo will be administered at a dosage of 10 ml in the morning.

Bottles of Neurotidine[®] and placebo oral solutions will be identical (same ingredients except for citicoline), containing 500 ml of a yellow solution with a measuring cup. Neurotidine[®] and placebo solutions will have similar taste. Each patient will be given the bottles for the first 3-month treatment period by the hospital pharmacist and will be asked to return them at the end

of the period (3 months). Then the patients will be given the other bottles for the next phase of the study (3 months): these will contain placebo if the patient received Neurotidine[®] in the first phase of the study and vice versa. Again, the patients will be asked to return after 3 months with the study bottles and will be given the last set of bottles for the final phase of the study (3 months): in this phase the bottle contents will be the same as in phase 2.

Information about compliance with treatment will be recorded at each visit. All study bottles will be collected and sent to the coordinating center.

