progression.⁶ However, some methodological flaws of the trial casted doubts on the validity of the findings and, as a matter of fact, brimonidine did not become the first-choice therapy for normal tension glaucoma (NTG) patients despite the evidence of a significant effect.

The action of citicoline in patients with neurodegenerative disorders has been known for a long time and today there are hundreds of publications about the efficacy of the molecule in patients with dementia, stroke, Parkinson's disease and glaucoma.² There is a systematic review from the Cochrane database reporting that citicoline can be effective in improving activity scores in patients with some stage of senile dementia.⁷ The mechanisms of action include “cell protection” (as it is part of the cell membrane), reduction of cell apoptosis and a positive effect on the synthesis of neurotransmitters – both dopaminergic and cholinergic.

Citicoline can be administered systemically (intramuscular, oral) and topically. Most of the literature on the effect of citicoline is based on systemic intramuscular administration.⁸ Since some years ago, similar bioavailability can be obtained with oral solution, a more practical and comfortable way of administration for chronic diseases where citicoline needs to be given daily for years.^{9,10} There is evidence that citicoline oral solution has 98% bioavailability.⁹ Recently, citicoline free acid has been authorized in Europe by the EFSA (European Food Safety Authority) as a Novel Food ingredient also for Special Medical Purpose, and according to this new classification, a form in oral solution (Neurotidine[®]) has been registered as Food for Special Medical Purpose with therapeutic Indication: “Glaucomatous patients with stable IOP, but with a progressive loss of Visual Field (VF)”. Citicoline eyedrops are also available in many European Countries.

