8.2 Exclusion Criteria

Patients must meet none of the following criteria to be eligible for the study:

- Single-eyed patients (visual acuity <0.1 in one eye).
- Patients without the psychophysical requirements to adequately participate and complete the trial.
- Patients with chronic angle-closure glaucoma (CACG) or other types of glaucoma.
- Patients with other ocular comorbidities interfering with the correct assessment of the glaucomatous damage to the VF.
- Patients who have undergone surgery within 6 months.
- Patients taking other potential neuroprotectors, including topical, competing with Neurotidine[®].
- Patients with Parkinson’s disease, dementia or a diagnosis of stroke in the last 6 months.

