10. DESIGN

The trial will be a randomized, double-masked, placebo-controlled, cross-over study. Eligibility criteria will be assessed, and study procedures clearly explained when the potentially eligible patients are initially visited. If the patients accept to participate in the trial, they will have to sign the informed consent form. After this, the patients will be randomized in a 1:1 ratio to one of the two sequences of the cross-over design: Neurotidine[®]-placebo or placebo-Neurotidine[®]. The randomization will be stratified by centre.

- Baseline visit (beginning of 1st period): Enrolled patients will undergo a complete ophthalmologic examination with VA, VF (24-2, SITA standard strategy), fundus assessment, biomicroscopy (with specific lens evaluation using Lens Opacities Classification System III (LOCS III) criteria), IOP assessment. A masked to treatment evaluator will administer the two study questionnaires (VFQ-25 and SF-36). The patients will be given the bottles for the first 3-month period.
- 3-month visit (end of the 1st period and beginning of 2st period): Patients will undergo a complete ophthalmologic examination with VA, VF (24-2, SITA standard strategy),

biomicroscopy, IOP assessment. Patients will be asked about treatment side effects and all complains/considerations will be recorded. The two study questionnaires (VFQ-25 and SF-36) will be administered. The patients will be given the bottles for the second 3-month period.

- 6-month visit: Patients will undergo a complete ophthalmologic examination with VA, VF (24-2, SITA standard strategy), biomicroscopy, IOP assessment. Patients will be asked about treatment side effects and all complains/considerations will be recorded. Patients will be again administered the 2 study questionnaires (SF-36 and VFQ-25). The patients will be given the bottles for the third 3-month phase.
- 9-month visit (end of the 2st period): Patients will undergo a complete ophthalmologic examination with VA, VF (24-2, SITA standard strategy), biomicroscopy, IOP assessment. Patients will be asked about treatment side effects and all complains/considerations will be recorded. Patients will be administered the two study questionnaires (VFQ-25 and SF-36).

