12.1.2 Database management and quality control

The CRO working on behalf of the Sponsor will review the data entered in the eCRF by investigational staff for completeness and accuracy and instruct site personnel to make any necessary corrections or additions. The Data Manager will perform the cleaning session by reviewing the warning messages raised by on-line checks and by running post-entry checks by means of validation programs and data listings specific for the study. The occurrence of any protocol deviations will also be checked.

If clarifications are needed, the Data Manager will raise queries through the web application. Designated investigator site staff will be required to respond to queries and the Data Manager will make the correction to the database according to the responses.

Data collection and query flows, as well as the on-line and off-line checks, are detailed in the Data Management Plan and Data Validation documents.

Concomitant medications and prior medications entered into the database will be coded using the WHO Drug Reference List, which employs the ATC classification system. Medical history/current medical conditions and AEs will be coded using MedDRA.

The database will be locked after all the above actions have been completed and the database has been declared complete and accurate.

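### Is the masking of the VFQ-25 left open because a masked evaluator is named only at baseline and the two products' ingredient lists differ?

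*Combined protocol and SAP*

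**What the plan says.** The protocol calls the trial double-masked in section 3 (Protocol Summary) and again at the start of section 10 (Design).

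- **Product.** Section 9 (Treatments) says that the bottles "will be identical (same ingredients except for citicoline), containing 500 ml of a yellow solution with a measuring cup". The two ingredient lists stand just above that sentence. Section 3 describes the placebo as not distinguishable in appearance and taste; section 9 claims only a similar taste.
- **Evaluator.** For the baseline visit, section 10 states: "A masked to treatment evaluator will administer the two study questionnaires (VFQ-25 and SF-36". For month 3 it states: "Patients will be asked about treatment side effects and all complains/considerations will be recorded. The two study questionnaires (VFQ-25 and SF-36) will be administered". For month 6: "Patients will be again administered the 2 study questionnaires (SF-36 and VFQ-25". For month 9: "Patients will be administered the two study questionnaires (VFQ-25 and SF-36". The three later entries name nobody as the administrator.
- **Earlier users of the product.** Section 8.2 excludes "Patients taking other potential neuroprotectors, including topical, competing with Neurotidine" and is silent on users of Neurotidine itself, although section 5 says that it "has been registered as Food for Special Medical Purpose with therapeutic Indication". Section 12.1.2 adds: "Concomitant medications and prior medications entered into the database will be coded using the WHO Drug Reference List".

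**The concern.** The primary outcome is a patient-reported score that staff administer, and each patient takes both products in turn and can compare them. The mask therefore matters more here than for a laboratory endpoint.

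Read literally, section 10 guarantees a masked evaluator only at the one visit where no product has yet been taken. At the three later visits it mentions the side-effect inquiry before the questionnaires. Anyone who has read section 9 knows that sucralose is in the placebo only, so a remark about taste might suggest the allocation to the person who then administers the VFQ-25. A patient who had used Neurotidine before the trial might recognise it unaided.

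At stake would be a difference between products that comes from expectation rather than from citicoline, and a report unable to say that the primary outcome was collected independently of such remarks.

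**Working it through.** **1. Ingredient lists (section 9).**

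| | Ingredients | Count |
|---|---|---|
| Shared | water, fructose, sodium citrate, sodium hydroxide, potassium sorbate, riboflavin | 6 |
| Active only | citicoline | 1 |
| Placebo only | sucralose, anhydrous citric acid | 2 |

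The active list has 6 + 1 = 7 items and the placebo list 6 + 2 = 8. The products differ by three listed ingredients, not one, so the sentence is wrong against the lists. That does not show a failed mask: extra placebo ingredients may be there to match taste or acidity, and both taste statements claim a match.

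**2. Who administers the questionnaires.** A masked evaluator is named at 1 of 4 questionnaire visits and at 0 of the 3 after treatment starts. If both periods' changes are taken from the month-0 score B (an assumption), then (Y2 − B) − (Y1 − B) = Y2 − Y1. The baseline score drops out, and the treatment contrast rests wholly on visits where the phrase is absent.

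**3. Is the absence deliberate?** Compare section 10 with section 4 (Schedule of Assessments). Section 4 marks the complete ophthalmological examination at all four visits, and its footnote includes fundus assessment and LOCS III lens grading. Section 10 spells out both at baseline and omits both at months 3, 6 and 9. The later entries are therefore abbreviated, and the evaluator phrase is lost in the same way. Section 4 also lists VFQ-25 and SF-36 above adverse events, the reverse of section 10. Neither list sets a visit sequence.

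**4. Would differing site practice bias the contrast?** If a centre's practice adds a constant c to every score, then (Y2 + c) − (Y1 + c) = Y2 − Y1. Only an effect that goes with the product matters, and the protocol gives no sign of one.

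**5. Scale.** Inputs from section 13: SD of differences 15.0, 100 per sequence, two-sided 0.05, difference 3.0.

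- Root MSE = 15/√2 = 10.607, as stated.
- SE = (15/2) × √(1/100 + 1/100) = 15/√200 = 1.061, with 198 df.
- Power for 3.0 points (noncentral t) = 80.4%, reproducing the stated 80%.
- With no true effect, a systematic difference between products of 0.31 points gives 6.0% rejection, 0.50 points gives 7.6%, and 0.70 points gives 10.1%.

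The 0.31 and 0.70 values were found by working back from 6% and 10%, and the 0.50 is a round number. Any trial with this SE would give the same rates, so they measure sensitivity and are not evidence of bias.

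**6. Earlier users.** The protocol gives no count. If 10% or 20% of 200 were earlier users (assumed), an analysis without them would keep 180 or 160 patients, with power for 3.0 points of 76.1% or 71.0%. It could only be supportive.

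**The case for a change.** The strongest case for a change is that section 10 opens with the double-masked label and still specifies a masked evaluator at baseline, so the authors thought the role worth stating. The label does not separate the person administering the questionnaires from the person who hears complaints, nor does it fix the order. Five centres could do this differently, and writing it down seems cheap.

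Part of this stands. The phrase would read better repeated at the later visits, the ingredient and taste statements do not agree with each other, and the eligibility of earlier Neurotidine users is unstated. Section 4 has concomitant medications recorded at all four visits, which may show current use, but the protocol does not say whether a food product would be entered there.

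The rest does not carry a change:

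- A separate evaluator who takes no part in side-effect, compliance or bottle-return procedures goes beyond what the baseline sentence requires. It needs a second staff member at three visits for about 200 patients.
- That evaluator would not address the more direct route. If a patient can tell the products apart, the patient's own answers are affected whoever asks the questions.
- The taste route assumes that sucralose makes the placebo recognisable, which the protocol nowhere says.
- Recording earlier use, or rerunning the model without earlier users, would describe a subgroup of unknown size. It would not correct any result shown to be wrong.

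**Conclusion.** No change to the plan is needed. The ingredient sentence in section 9 is a clerical slip against its own lists, and the two taste descriptions differ only in wording; they can be reconciled in an ordinary document correction. The missing evaluator phrase at months 3, 6 and 9 is abbreviation in a trial declared double-masked, and the sensible reading is that the same masked role continues. Sites can also give the questionnaires before the side-effect inquiry without any amendment. Whether earlier Neurotidine users may enter is a clarification the sponsor can give if asked.

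No sample size, power or significance figure changes: the SE stays at 1.061 points and power at 80.4%. This rests on two readings: that the double-masked statement covers whoever administers the questionnaires after baseline, and that the products match in appearance and taste as claimed. The protocol contradicts neither. Direct evidence that patients or staff could identify the product would reopen the question.

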10. DESIGN

The trial will be a randomized, double-masked, placebo-controlled, cross-over study. Eligibility criteria will be assessed, and study procedures clearly explained when the potentially eligible patients are initially visited. If the patients accept to participate in the trial, they will have to sign the informed consent form. After this, the patients will be randomized in a 1:1 ratio to one of the two sequences of the cross-over design: Neurotidine[®]-placebo or placebo-Neurotidine[®]. The randomization will be stratified by centre.

- Baseline visit (beginning of 1st period): Enrolled patients will undergo a complete ophthalmologic examination with VA, VF (24-2, SITA standard strategy), fundus assessment, biomicroscopy (with specific lens evaluation using Lens Opacities Classification System III (LOCS III) criteria), IOP assessment. A masked to treatment evaluator will administer the two study questionnaires (VFQ-25 and SF-36). The patients will be given the bottles for the first 3-month period.
- 3-month visit (end of the 1st period and beginning of 2st period): Patients will undergo a complete ophthalmologic examination with VA, VF (24-2, SITA standard strategy),

biomicroscopy, IOP assessment. Patients will be asked about treatment side effects and all complains/considerations will be recorded. The two study questionnaires (VFQ-25 and SF-36) will be administered. The patients will be given the bottles for the second 3-month period.

- 6-month visit: Patients will undergo a complete ophthalmologic examination with VA, VF (24-2, SITA standard strategy), biomicroscopy, IOP assessment. Patients will be asked about treatment side effects and all complains/considerations will be recorded. Patients will be again administered the 2 study questionnaires (SF-36 and VFQ-25). The patients will be given the bottles for the third 3-month phase.
- 9-month visit (end of the 2st period): Patients will undergo a complete ophthalmologic examination with VA, VF (24-2, SITA standard strategy), biomicroscopy, IOP assessment. Patients will be asked about treatment side effects and all complains/considerations will be recorded. Patients will be administered the two study questionnaires (VFQ-25 and SF-36).

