13. SAMPLE SIZE

The sample size has been calculated based on the main outcome of the study, i.e. the mean change vs baseline of the global score of The National Eye Institute 25-Item Visual Function Questionnaire (VFQ-25) in patients with moderate-stage glaucoma (*Ophthalmol 2015 Nov Acta 19*).

When the sample size in each sequence group is 100, (a total sample size of 200) a 2 x 2 crossover design will have 80% power to detect a difference in means of 3.0 (the difference between study treatment mean, μ_1 , of 3.0 and placebo mean, μ_2 , of 0) assuming that the crossover ANOVA \sqrt{MSE} is 10.607 (the standard deviation of differences, σ_d , is 15.0) using a two group t-test (crossover ANOVA) with a 0.05 two-sided significance level.

The total sample size is adjusted to 220 patients considering an expected dropout rate of about 10%.

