14. STATISTICAL ANALYSIS

Continuous data will be summarized with standard descriptive statistics (i.e. the mean, standard deviation, minimum, median and maximum, 95% confidence limits). Categorical data will be summarized by frequencies and percentages.

No statistical test will be performed for between-group differences in demographic and baseline features (medical history and efficacy data).

Medical history and adverse events will be described according to System Organ Classes (SOC) and Preferred Terms (PT) using the Medical Dictionary for Regulatory Activities (MedDRA) and will be presented by treatment group.

Previous/concomitant medications will be presented by treatment group using the World Health Organization Drug Dictionary (WHO-DD).

[figure not shown]
The primary efficacy variable will be analysed using crossover ANOVA, considering sequence, subjects, period and treatment as sources of variation.

All study centers will fill in a web-based e-CRF. The Data Center will check the e-CRF and solve all the queries. The Coordinating Center will do the statistical analysis of collected data.

The association between quality of life and measures of visual symptoms, of the ability to perform vision-related activities and clinical findings will be analysed by means of linear regression models.

All analysis will be performed using SAS version 9.4.

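### Randomisation is stratified by centre, but the primary crossover ANOVA has no centre-by-period term, so any centre-specific shift between periods stays in the error term

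*Combined protocol and SAP*

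**What the plan says.** Section 10 (Design) allocates patients 1:1 to the two sequences and adds: "The randomization will be stratified by centre". Section 14 (Statistical analysis) gives the primary model in one sentence: "The primary efficacy variable will be analysed using crossover ANOVA, considering sequence, subjects, period and treatment as sources of variation". Neither centre nor centre-by-period is listed there or in any other analysis statement.

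Section 13 (Sample size) says that, with 100 patients per sequence, the "crossover design will have 80% power to detect a difference in means of 3.0". It assumes an SD of within-patient differences of 15.0 (root MSE 10.607) and a two-sided 5% test, and makes no allowance for centre. Section 16.10 refers to five enrolling centres. Section 8 aims for 40 patients in each, with limits of 20 and 50, and competitive enrolment.

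**The concern.** In a two-period crossover, the treatment test compares within-patient period differences between the two sequences. Anything constant within a patient cancels from that difference, including the level of the patient's centre. A change between periods shared by the patients of one centre does not cancel. It could arise from a change of questionnaire evaluator at a site, a local change in IOP-lowering practice, or a difference in calendar time.

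Stratified randomisation spreads such shifts roughly evenly over the two sequences, so they hardly disturb the treatment estimate. A model without a centre-by-period term nevertheless counts them as residual error. The trial then obtains the balance that stratification provides but does not credit it in the standard error. At stake are a little power and a test that runs somewhat below its nominal 5% level.

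**Working it through.** **Inputs.** From Section 13: 100 per sequence, difference 3.0, SD of within-patient differences 15.0, two-sided alpha 0.05. From Section 16.10: five centres. From Section 8: 40 per centre as the target. Assumed, because the documents give no value: the SD τ of the centre shift in the within-patient period difference, taken as 0, 3 and 5. The 15.0 is treated as the total SD, including any such shift.

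**1. The plan's own figure.** The root MSE is 15/√2 = 10.607, as stated. The treatment estimate is half the difference between sequences in mean period difference:

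- SE = (15/2) × √(1/100 + 1/100) = 1.061
- Noncentrality = 3.0/1.061 = 2.83
- Noncentral t with 198 df: power 80.4%

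The stated 80% reproduces.

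**2. Cost of the term if centres do not differ.** Five centres use 5 − 1 = 4 df, so error df fall from 198 to 194. The critical t moves from 1.9720 to 1.9723, and power falls by 0.008 points. If sequences are uneven within centres, the SE is multiplied by √(50/Σ[ab/(a+b)]), where a and b are the sequence counts in each centre:

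- Splits 21:19, 19:21, 22:18, 18:22, 20:20: the sum is 49.75, the factor 1.0025, and power 80.2%.
- Splits 12:8, 23:27, 27:23, 18:22, 20:20: the sum is 49.54, the factor 1.0046, and power 80.0%.

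The cost in these cases is about 0.2 to 0.4 points.

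**3. How far the unadjusted standard error is too large.** With balance within centres, the sampling variance of the estimate depends only on 225 − τ². The unadjusted residual also contains the between-centre sum of squares, whose 4 df each carry an extra 40τ². Its expected value is therefore (225 − τ²) + 4 × 40τ²/198.

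- τ = 3: 216 + 7.3 = 223.3 against 216. The SE is too large by √(223.3/216) = 1.017, about 2%.
- τ = 5: 200 + 20.2 = 220.2 against 200. The SE is too large by √(220.2/200) = 1.049, about 5%.

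**4. Power and type I error.** With the term, the noncentral t formula on 194 df uses SD √216 = 14.70 (τ = 3) and √200 = 14.14 (τ = 5). The SEs are 1.039 and 1.000, and power is 81.9% and 84.7%. Simulation of both models (200 patients, five centres, balanced sequences, total SD 15) gave:

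| τ | Share of 225 | Power without term | Power with term | Gain (points) |
|---|---|---|---|---|
| 0 | 0% | 80.1% | 80.0% | nil |
| 3 | 4% | 81.3% | 82.0% | 0.7 |
| 5 | 11% | 82.2% | 84.6% | 2.4 |

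At τ = 5 the type I error was 4.0% without the term and 5.0% with it. A second simulation (40,000 runs per setting, error about 0.2 points for power), set by variance share, agrees. At a 5% share power was 80.8% against 81.9%, and at 10% it was 82.0% against 84.1%. Type I error without the term was 4.5% and 4.2%.

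**The case against.** The strongest case against is that the benefit rests entirely on a variance component that the documents do not give. At τ = 5, centre shifts would have an SD larger than the 3.0-point effect the trial is designed to detect, and nothing in the documents supports that. The possible causes are also uncertain. An evaluator who stays the same cancels within patient. Season follows each patient's own enrolment date. IOP-lowering drugs are chosen by the treating clinician (Section 9), so changes may be largely individual. All of this stands, and it is why the gain is given as a range starting at nil.

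A reader might infer that the analysis ignores centre altogether. It does not: each patient belongs to one centre, so the subjects term contains the centre main effect, and adding centre alone would change nothing in the treatment test.

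A reader might also compare power with the term (about 82% and 85%) with a fixed 80% without it. That overstates the gain. Stratification steadies the unadjusted estimate too, so unadjusted power also rises with τ, as the table shows.

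Nor is the term free. Section 10 gives no block size and centres may differ in size, so exact balance within centres is not assured, and the loss of up to about 0.4 points applies if centres do not differ.

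**Conclusion.** The point holds as a minor efficiency refinement. The stratification factor enters the primary model only through subjects, and its interaction with period is left in the residual. The result is a standard error that is somewhat too large and a slightly conservative test. With sequences balanced within centres there is no bias in the treatment estimate.

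The net gain from the term is nil at τ = 0, about 1 power point at τ = 3 and about 2.5 at τ = 5. These figures assume five centres of 40, balanced sequences and a total SD of 15.0.

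A reader might infer that the omission leaves the trial short of its planned power. The documents do not support that: Section 13 uses the same unadjusted analysis, its 80% reproduces, and with 15.0 taken as the total SD any centre-by-period variation is already inside it.

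**What to change.** In Section 14, add centre-by-period to the primary model's sources of variation. A separate centre main effect is not needed, because subjects contain it. Equivalently, compare within-patient period differences between the two sequences with centre as a factor. State this before unmasking, so that adjustment for centre is not left to a later choice.

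The cost is one sentence in the plan and the 4 error df, with the small power cost given above. With a minimum of 20 patients per centre the term is readily estimable. No additional patients, visits or data are needed, and the sample size in Section 13 can stay as it is.
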